## 8.4. Study setting and data sources

This study will be conducted using routinely collected data from primary and secondary care data sources in the DARWIN EU® network of data partners from 3 European countries, of 3 EU member states. All data were *a priori* mapped to the OMOP CDM.

Table 1. Data sources.

Country	Name of data source	Health care setting	Type of data	Number of active individuals	Calendar period covered by each data source	Contributing to
France	CDW Bordeaux	Hospital care	EHR	247,200	2005 – 09/2025	All objectives
Germany	IQVIA DA Germany	Outpatient General Practitioner and Specialist Care	EHR	4,484,200	1989 – 12/2024	All objectives
United Kingdom	CPRD GOLD	Outpatient General Practitioner Care	EHR	2,632,700	1987 – 05/2025	All objectives

CDW Bordeaux = Clinical Data Warehouse of Bordeaux University Hospital; CPRD GOLD = Clinical Practice Research Datalink GOLD; EHR = electronic health records; IQVIA DA Germany = IQVIA Disease Analyzer Germany. Number of active individuals is defined as the number of individuals present in the last six months of the respective data source.

1. France: Clinical Data Warehouse of Bordeaux University Hospital (CDW Bordeaux)
2. Germany: IQVIA Disease Analyzer Germany (IQVIA DA Germany)
3. United Kingdom: Clinical Practice Research Datalink GOLD (CPRD GOLD)

### Data sources selection

These data sources fulfil the criteria required in terms of data quality, completeness, timeliness, and representativeness for a drug utilisation and characterisation studies while covering different regions of Europe ([Annex II](#)).

## 8.5. Study period

The study period is from 01/01/2017 to 31/12/2024. The data availability of the included data sources aligns with the study period.

## 8.6. Variables

### 8.6.1. Exposure

For *objective 1*, the primary exposure is defined as a prescription or dispensing record of a prespecified immunoglobulin drug (ingredient level). For *objective 2*, prescriptions of all prespecified immunoglobulin brands of an individual during the study period will be included. For *objectives 3 and 4*, the prescription or dispensing record of prespecified immunoglobulin brands represents the first recorded prescription in the study period and individuals from primary care data sources were required to have no prior immunoglobulin use in the 180 days prior the index date.

To define treatment episodes, sequential prescriptions will be grouped into drug eras, allowing a maximum gap of 30 days between the end of one prescription and the start of the next. More details about the definition of a treatment episode are provided in [Section 8.8.3](#).

The preliminary concept sets used for the identification of exposures are described in [Annex IV](#). These codes will be refined during the study execution following the DARWIN EU® phenotyping standard processes, which involve the review of code lists, and the review of phenotypes after their execution in the participating data sources. Final concept sets will be defined following input from EMA.

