Active substance	Immunoglobulins: respiratory syncytial virus immune globulin intravenous, immunoglobulin G, freeze-dried pepsin-treated human normal immunoglobulin, pH4-treated acidic human normal immunoglobulin, pH4-treated acidic human normal immunoglobulin (for s.c. injection), polyethylene glycol-treated human normal immunoglobulin, freeze-dried pH4-treated human normal immunoglobulin, freeze-dried sulfonated human normal immunoglobulin, freeze-dried polyethylene glycol-treated human normal immunoglobulin, immunoglobulin M human, immunoglobulin A, Rho(D) immune globulin, tetanus immune globulin, varicella-zoster immune globulin, hepatitis B immune globulin, rabies immune globulin human, Immunoglobulin Anti-Rubella, human vaccinia immune globulin, staphylococcus epidermidis immunoserum rabbit, staphylococcus aureus immunoserum, cytomegalovirus immune globulin, diphtheria antitoxin, hepatitis A immunoglobulin (systemic), Immunoglobulin Anti-Tickborne Encephalitis, pertussis immunoglobulin; systemic, measles immunoglobulin; systemic mumps immunoglobulin; systemic, anthrax immune globulin, Bacillus anthracis immunoserum rabbit, Nebacumab, raxibacumab, bezlotoxumab, obiltoxaximab, palivizumab, MOTAVIZUMAB, tixagevimab, ansuvimab, sotrovimab, REGDANVIMAB, casirivimab, nirsevimab, Sipavibart
Medicinal product	Immunoglobulin brands: Flebogamma DIF, Kiovig, Privigen, Octagam, Yimmugo, Ig vena, Intratect, Iqymune, Panzyga/Globiga, Gamunex, Hizentra, Hyqvia, Cuvitru, Cutaquig, Xembify, Gammagard, Nanogam/Optiglobin, Clairyg, Tegeline, Pentaglobin, Keycute/Naxiglo, Gammaplex, Beriglobin, Rhesonativ, Rhophylac

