## 6. RATIONALE AND BACKGROUND

Immunoglobulins are purified products from plasma of human donors. They can be routinely administered as replacement therapy in immunodeficient patients or are used as immunomodulating doses to treat various immune-related and inflammatory diseases.[1, 2] Immunoglobulins are not only used for authorised indications, such as primary immunodeficiency disorders and Kawasaki disease, but also for unauthorised (off-label) indications.[3] Prolonged low levels of certain immunoglobulins can increase the risk of certain infections and replenishment of these immunoglobulins can reduce this risk.[4] The global demand of immunoglobulins increases every year, resulting in intermittent shortages that could affect individuals with conditions that have limited alternative treatments.[1, 3] This study aims to generate real-world evidence on the treatment and characteristics of individuals receiving immunoglobulins.

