### 8.8.3. Statistical model specification and assumptions of the analytical approach considered

#### Objective 1

Trends of immunoglobulin use during the study period will be assessed based on OMOP CDM mapped data using the *IncidencePrevalence* R package (<https://github.com/darwin-eu/IncidencePrevalence>), developed by DARWIN EU®.

The prevalence of individuals with a recorded immunoglobulin prescription (expressed as the proportion of individuals with any immunoglobulin prescription in the general study population) will be presented by immunoglobulin ingredient, route of administration, and stratified by sex and age.

Prevalence will be calculated as overall and annual, which summarises the total number of individuals with recorded immunoglobulin use during a given period divided by the population at risk of receiving immunoglobulins during that period. Therefore, period prevalence will give the proportion of individuals exposed at any time during a specified interval. Binomial 95% confidence intervals will be calculated.

#### Objective 2

Trends of immunoglobulin use during the study period will be assessed based on OMOP CDM mapped data using the *IncidencePrevalence* R package (<https://github.com/darwin-eu/IncidencePrevalence>), developed by DARWIN EU®.

The quarterly prevalence of individuals with prescriptions for prespecified immunoglobulin brands will be estimated (expressed as the proportion of individuals prescribed each specific immunoglobulin brand among prevalent immunoglobulin users).

Prevalence will be calculated as quarterly period prevalence, which summarises the total number of individuals with recorded immunoglobulin brand prescription during a quarter divided by the population of prevalent immunoglobulin users during that period. Therefore, period prevalence will give the proportion of individuals exposed to a specific brand at any time during the specified interval. Binomial 95% confidence intervals will be calculated.

An illustration of the calculation of period prevalence is shown below in **Figure 3**. Between time  $t+2$  and  $t+3$ , two of the five study participants receive immunoglobulin treatment, giving a prevalence of 40%. Meanwhile, for the period  $t$  to  $t+1$  all five also had some observation time during the year with one of the five study participants having a recorded immunoglobulin prescription, giving a prevalence of 20%.

[figure not shown]

Figure 3. Prevalence example.

### Objective 3

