Immunoglobulin brand A						
Pre-specified antibiotic A						
Pre-specified antibiotic B						
Pre-specified antibiotic C/D/E, etc.						
Immunoglobulin brand B/C/D, etc.						
Pre-specified antibiotic A						
Pre-specified antibiotic B						
Pre-specified antibiotic C/D/E, etc.						

- Mock figure: Annual prevalence of immunoglobulin use, overall and stratified by ingredient, per data source.

In addition to the mock figure above, the following figures will also be provided:

- 'Annual prevalence of immunoglobulin use, stratified by ingredient and route of administration, per data source'
- Annual prevalence of immunoglobulin use, stratified by ingredient and sex, per data source'
- 'Annual prevalence of immunoglobulin use, stratified by ingredient and age group, per data source'
- 'Quarterly prevalence of immunoglobulin brands, per data source'

An interactive dashboard will be generated by incorporating all the results (tables and figures) included in the PDF report mentioned above.

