pertussis immunoglobulin	pertussis immunoglobulin; systemic	Immunoglobulins	J06BB13	21601271	Yes
measles immunoglobulin	measles immunoglobulin; systemic	Immunoglobulins	J06BB14	21601272	Yes
Mumps immunoglobulin	mumps immunoglobulin; systemic	Immunoglobulins	J06BB15	21601273	Yes
anthrax immune globulin	anthrax immune globulin	Immunoglobulins	J06BB19	35605786	Yes
Bacillus anthracis immunoserum rabbit	Bacillus anthracis immunoserum rabbit	Immunoglobulins	J06BB19	42903978	Yes
Nebacumab	Nebacumab	Immunoglobulins	J06BC01	40798985	Yes
raxibacumab	raxibacumab	Immunoglobulins	J06BC02	43013193	Yes
bezlotoxumab	bezlotoxumab	Immunoglobulins	J06BC03	1718211	Yes
obiltoxaximab	obiltoxaximab	Immunoglobulins	J06BC04	35603994	Yes
palivizumab	palivizumab	Immunoglobulins	J06BD01	537647	Yes
MOTAVIZUMAB	MOTAVIZUMAB	Immunoglobulins	J06BD02	36851985	Yes
tixagevimab	tixagevimab	Immunoglobulins	J06BD03	702418	Yes
ansuvimab	ansuvimab	Immunoglobulins	J06BD04	739418	Yes
sotrovimab	sotrovimab	Immunoglobulins	J06BD05	1536976	Yes
REGDANVIMAB	REGDANVIMAB	Immunoglobulins	J06BD06	36858135	Yes
casirivimab	casirivimab	Immunoglobulins	J06BD07	37003288	Yes

Substance Name	Concept name	Class	ATC code	Ingredient Concept ID	Include descendants
nirsevimab	nirsevimab	Immunoglobulins	J06BD08	746155	Yes
Sipavibart	Sipavibart	Immunoglobulins	J06BD09	1253346	Yes
Tetracyclines	Tetracyclines	Antibiotics	J01A	21602797	Yes
Amphenicols	Amphenicols	Antibiotics	J01B	21602813	Yes
Beta-lactam antibacterials, penicillins	Beta-lactam antibacterials, penicillins	Antibiotics	J01C	21602818	Yes
Other beta-lactam antibacterials	Other beta-lactam antibacterials	Antibiotics	J01D	21602868	Yes
Sulfonamides and trimethoprim	Sulfonamides and trimethoprim	Antibiotics	J01E	21602929	Yes
Macrolides, lincosamides and streptogramins	Macrolides, lincosamides and streptogramins	Antibiotics	J01F	21602968	Yes
Aminoglycoside antibacterials	Aminoglycoside antibacterials	Antibiotics	J01G	21602990	Yes
Quinolone antibacterials	Quinolone antibacterials	Antibiotics	J01M	21603006	Yes
Other antibacterials	Other antibacterials	Antibiotics	J01X	21603041	Yes

List of immunoglobulins brands concepts definition is provided in the table below:

Table S4. Preliminary list of immunoglobulin brand definitions.

Brand Name	Concept name	Concept ID	Include descendants
Flebogamma DIF	Immunoglobulin G Injectable Solution [Flebogamma DIF]	35745366	Yes
Flebogamma DIF	Immunoglobulin G Injection [Flebogamma DIF]	21085351	Yes

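### Objective 1's pooled immunoglobulin prevalence counts antibody products and rabbit sera, although the rationale concerns human-plasma products, and no plasma-derived total is planned

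*Protocol*

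**What the plan says.** Section 6 describes the product class: "Immunoglobulins are purified products from plasma of human donors". It gives the motive: "The global demand of immunoglobulins increases every year, resulting in intermittent shortages".

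Section 8.6.1 sets the objective 1 exposure: "the primary exposure is defined as a prescription or dispensing record of a prespecified immunoglobulin drug (ingredient level"). The ingredients are those in the front-page active substance field and in Annex IV, Table S3. The front-page list ends with "Nebacumab, raxibacumab, bezlotoxumab, obiltoxaximab, palivizumab, MOTAVIZUMAB, tixagevimab, ansuvimab, sotrovimab, REGDANVIMAB, casirivimab, nirsevimab, Sipavibart". Table S3 carries the same products with the class label Immunoglobulins; the first of their rows reads "Nebacumab Nebacumab Immunoglobulins J06BC01".

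Section 8.8.3 defines the prevalence as "the proportion of individuals with any immunoglobulin prescription in the general study population". Section 8.8.4 plans a figure titled "Annual prevalence of immunoglobulin use, overall and stratified by ingredient, per data source", with further figures by ingredient crossed with route, sex and age group.

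No output groups the ingredients into plasma-derived and other products, and Section 9 does not mention the mix. Section 8.6.1 calls the concept sets preliminary and leaves their final form to input from EMA.

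**The concern.** The rationale and the exposure list describe different classes. Someone reading the pooled annual curve after Section 6 would take it as a measure of use of human-plasma products, the products whose supply is at issue. The curve also counts people whose only record is an antibody product or a rabbit serum. Its level can then exceed plasma-derived use. Its slope can also change because the share of such people changes, with plasma-derived use unchanged.

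Objectives 2 to 4 look at brands. Table S4 defines these through immunoglobulin G, immunoglobulin M, human immunoglobulin and Rho(D) concepts and contains none of the antibody products. The pooled objective 1 figure therefore covers a wider class than the rest of the study describes.

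**Working it through.** The Protocol states no figure to reproduce here. The check is a count of the exposure list, followed by a sensitivity calculation over an assumed range.

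**Step 1: count the Table S3 rows labelled Immunoglobulins, by ATC code.**

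| ATC group | Rows |
|---|---|
| J06B (RSV immune globulin intravenous) | 1 |
| J06BA | 10 |
| J06BB | 18 |
| J06BC | 4 |
| J06BD | 9 |
| Total | 42 |

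Antibody products: 4 + 9 = 13, and 13/42 = 31%. They are read as such from their names (twelve end in -mab, one in -bart) and their separate ATC groups; the Protocol does not describe their origin. Two J06BB rows are named as rabbit: the staphylococcus epidermidis serum and one of the two anthrax products. Together 13 + 2 = 15, and 15/42 = 36%, which leaves 27 rows. The origin of the staphylococcus aureus immunoserum and the diphtheria antitoxin is not stated, so they are not counted among the 15. These are shares of list rows, not of users.

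**Step 2: effect on the level.** Let s be the share of pooled users in a period whose only records are for non-plasma products. Plasma-derived prevalence is (1 - s) times the pooled figure, so the relative excess of the pooled figure is 1/(1 - s) - 1.

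| Assumed s | Excess |
|---|---|
| 1% | 1.0% |
| 5% | 5.3% |
| 10% | 11.1% |
| 20% | 25.0% |

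**Step 3: effect on the trend.** If plasma-derived prevalence is flat and s moves from a to b, the pooled figure changes by (1 - a)/(1 - b) - 1.

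| Assumed a to b | Apparent rise |
|---|---|
| 0% to 5% | 5.3% |
| 2% to 10% | 8.9% |
| 5% to 20% | 18.8% |

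The feasibility counts (10,900 in CDW Bordeaux, 47,500 in IQVIA DA Germany, 73,600 in CPRD GOLD) are not split by ingredient. The Protocol therefore gives no basis for choosing a value of s.

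**Step 4: can the planned output recover the plasma-derived total?** One person can have several ingredients in a year, so adding ingredient prevalences counts that person more than once. Counts below 5 are suppressed. Under Annex III the sites return aggregated files only. A person-level plasma-derived total would therefore need code to be rerun at every site.

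**The case against.** The scope is deliberate and disclosed. The front page names every one of these ingredients and Table S3 gives each an ATC code, so objective 1 measures what its list says it measures. That stands: the antibody rows are not stray codes, and a reader who inferred a coding mistake would be wrong. What remains is that the background sentence and the list are not reconciled.

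The ingredient strata also do much of the work. An antibody product with enough users to move the total would appear in its own series. The immunoglobulin G row is itself a person-level figure that approximates use of normal immunoglobulin, since Table S4 maps most brands to it. This reduces the harm but does not remove it. That row is one of ten J06BA rows, and Table S4 also places some Rhesonativ and Rhophylac concepts under immunoglobulin G. It is neither a clean normal-immunoglobulin total nor a plasma-derived one.

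Three further inferences are tempting and should not be drawn:

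- That the antibody products entered or left the market during 2017 to 2024 and so must distort the trend. The Protocol gives no dates of use for them.
- That 31% or 36% of users are affected. Some listed rows may have no users at all.
- That one antibody product within 180 days bars a primary-care patient from objectives 3-4. Section 8.3 requires no prior immunoglobulin exposure but does not say which list defines it. The only code-list pointer under those criteria is to the brand list.

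Finally, the concept sets are preliminary. That makes a change easy, but nothing in the text commits to this regrouping.

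**Conclusion.** The point holds as a mismatch of definition that reaches a planned headline figure. At least 15 of the 42 ingredients pooled as immunoglobulin use lie outside the rationale's own description, no plasma-derived composite is planned, and the limitations are silent on it.

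The numerical effect is unknown. On the assumption that 1% to 20% of pooled users had only such products, the excess is 1% to 25%; in these three sources it could be small. It would be too strong to say that the headline fails to measure the intended class, or that its trend is biased, because nothing in the Protocol shows how many users are involved.

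A related gap is the undefined scope of two other populations. For objective 2, the abstract's population has any immunoglobulin record, while Section 8.3 requires a record of a prespecified brand. For the objectives 3-4 washout, the list is unnamed.

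**What to change.** Add prespecified person-level composites to objective 1, built from the existing codes:

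1. Human plasma-derived immunoglobulins as the headline: the human entries of J06B (including the RSV immune globulin row, which a rule limited to J06BA and J06BB would drop), J06BA and J06BB.
2. Human normal immunoglobulin (J06BA), because the first composite still mixes normal with specific products such as Rho(D) and tetanus.
3. Antibody products (J06BC, J06BD) and animal sera as a separate group.

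Keep the all-J06B total, labelled as such, and keep the ingredient rows. State the origin of the staphylococcus aureus immunoserum and the diphtheria antitoxin so that each can be assigned. Name the list that defines prior immunoglobulin exposure in objectives 3-4 and prevalent immunoglobulin users in objective 2. Add a sentence to Sections 6 and 9 explaining how the listed class relates to plasma products.

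The cost is a few extra cohort definitions, some more output, and a headline that may be somewhat lower. It is best done before the code is run at the sites.

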### 8.6.2. Outcome

The outcomes of interest are as follows:

- Prevalence of individuals with a recorded immunoglobulin prescription among the general population, including type of immunoglobulin, route of administration (*objective 1*).
- Prevalence of individuals with a prespecified immunoglobulin brands prescription among prevalent immunoglobulin users (*objective 2*).
- Initial and cumulative dose, number of prescriptions, and treatment duration of prespecified immunoglobulin brands among treatment initiators (*objective 3*).
- Characterisation of individuals initiating treatment with prespecified immunoglobulin brands (*objective 4*).

### 8.6.3. Covariates, including confounders, effect modifiers, and other variables

The variables for *objective 1* are as follows:

- Calendar period
  - Year
- Route of administration:
  - Intravenous
  - Subcutaneous
  - Intramuscular
  - Other
  - Missing
- Age groups, defined at cohort entry date:
  - Overall population
  - 1 to 18 years
  - 19 to 65 years
  - >65 years and older
- Sex, defined at cohort entry date:
  - Overall
  - Male
  - Female

The variables for *objective 2* are as follows:

- Calendar period
  - Quarter of year
- Prespecified brands, including (if available):
  - Flebogamma DIF
  - Kiovig
  - Privigen
  - Octagam (5% and 10%)
  - Yimmugo
  - Ig vena
  - Intratect
  - Iqymune
  - Panzyga/Globiga
  - Gamunex
  - Hizentra
  - Hyqvia
  - Cuvitru
  - Cutaquig
  - Xembify
  - Gammagard
  - Nanogam/Optiglobin
  - Clairyg
  - Tegeline
  - Pentaglobin
  - Keycute/Naxiglo
  - Gammaplex
  - Beriglobin
  - Rhesonativ
  - Rhophylac

The variables for characterisation of immunoglobulin users (*objective 4*) are as follows:

- Demographics, at index date:
  - Sex: Female/male
  - Age
  - Age group: 1 to 18 years, 19 to 65 years, >65 years and older

- Indication for use: Prespecified conditions will be used as proxies to assess the indication for immunoglobulin use, including both authorised and non-authorised indications. The assessment windows will be any time prior to 7 days after the index date [-inf, +7], 30 days prior to 7 days after the index date [-30, +7], and 7 days prior to 7 days after the index date [-7, +7].
  - Primary immunodeficiency syndrome, including:
    - Primary immunodeficiency syndromes
  - Secondary immunodeficiencies, including:
    - Secondary immunodeficiencies
  - Neurology, including:
    - Guillain Barré syndrome (GBS)
    - Chronic inflammatory demyelinating polyradiculoneuropathy (CIDP)
    - Multifocal motor neuropathy (MMN)
    - Myasthenia gravis
    - Stiff person syndrome
    - Lambert-Eaton myasthenia syndrome
  - Haematology, including:
    - Immune thrombocytopenia (ITP)
    - Acquired von Willebrand disease
    - Foetal Neonatal Alloimmune Thrombocytopenia (FNAIT)
  - Infectious diseases, including:
    - Measles
  - Solid organ transplantation, including:
    - Transplantation
  - Internal medicine, including:
    - Kawasaki's disease
    - Inflammatory myopathy
    - (Juvenile) dermatopolymyositis
    - ANCA vasculitis (replacement therapy)
    - Systemic lupus erythematosus (SLE)
  - Hepatology, including:
    - Hepatitis A
  - Other indications, which will be assessed overall and separately for each indication, where available, including:
    - Oncology
    - Autoimmune or paraneoplastic encephalitis
    - Epilepsy

- Progressive systemic sclerosis
  - Sjögren syndrome
  - COVID-19
  - Alzheimer
- Comorbidities: The top 10 most frequent diagnostic codes (comorbidities) will be identified through large-scale characterisation. These will be assessed 30 days prior to the index date [-30, 0], 1 year prior to the index date [-365, 0], and any time prior the index date [-inf, 0].

Common infections: Prespecified common infections among individuals initiating treatment with prespecified immunoglobulin brands will be assessed up to 30 days post-index [0, +30] and up to 365 days post-index [0, +365]. The following types of infections [4] will be assessed:

- Systemic infections, including:
  - Gram negative sepsis
  - Bacteraemia
- Bacterial infections, including:
  - Bacterial infectious disease
- Central nervous system infections, including:
  - Meningitis
- Respiratory & ear, nose, throat, ocular infections, including:
  - Otitis
  - Conjunctivitis
  - Bronchitis
  - Sinusitis
  - Respiratory tract infections
- Fungal infections, including:
  - Opportunistic mycosis
  - Invasive fungal infection
- Gastrointestinal & intra-abdominal infections, including:
  - Acute diarrhoea
  - Gastrointestinal infections
  - Peritonitis
- Urinary infections, including:
  - Urinary tract infections
- Viral infections:
  - Chronic enteroviral infections
  - Herpesvirus infections

- Antibiotic treatment: Exposure to prespecified antibiotics will be assessed up to 30 days post-index [0, +30] and up to 365 days post-index [0, +365]. The following classes of antibiotic ingredients will be assessed:
  - Tetracyclines
  - Amphenicols
  - Beta-lactam antibacterials, penicillins
  - Other beta-lactam antibacterials
  - Sulphonamides and trimethoprim
  - Macrolides, lincosamides, and streptogramins
  - Aminoglycoside antibacterials
  - Quinolone antibacterials
  - Other antibacterials

The preliminary concept sets used for the identification of covariates are described in [Annex IV](#). Final concept sets will be defined following input from EMA.

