## 8. RESEARCH METHODS

### 8.1. Study design

A cohort study will be conducted using routinely collected health data from 3 data sources from 3 countries across Europe and in 3 EU member states. The study will comprise of:

- A population-level drug utilisation study which will be conducted to address *objectives 1* and *2*, assessing the prevalence of individuals with a recorded immunoglobulin prescription, stratified by type of immunoglobulin and route of administration, among the general population (**Figure 1a**) and the prevalence of prespecified immunoglobulin brands among individuals with an immunoglobulin prescription (**Figure 1b**).
- A patient-level drug utilisation study which will be conducted to address *objectives 3* and *4*, assessing treatment characteristics and clinical characteristics of individuals initiating treatment with prespecified immunoglobulin brands, including dose, treatment duration, number of prescriptions, and indication for use, comorbidities, and common infections and antibiotics prescribed (**Figure 2**).

[figure not shown]

Figure 1a. Graphical depiction of the study design *objective 1*.

- Stratification by sex or age group (i) 1 to 18 years, ii) 19 to 65 years, and iii) >65 years and older) will be done at cohort entry date.
- Earliest of: 1) loss to follow-up, 2) death, 3) end of observation period (the latest available data), or 4) study end date 31/12/2024.

[figure not shown]

Figure 1b. Graphical depiction of the study design *objective 2*.

- Earliest of: 1) loss to follow-up, 2) death, 3) end of observation period (the latest available data), or 4) study end date 31/12/2024.

[figure not shown]

Figure 2. Graphical depiction of the study design *objectives 3–4*.

- a. Criterion only applies for primary care data sources (IQVIA DA Germany and CPRD GOLD)
- b. Indication for use include the following prespecified indication groups 1) primary immunodeficiency syndrome, 2) secondary immunodeficiencies, 3) neurology, 4) haematology, 5) infectious diseases, 6) solid organ transplantation, 7) internal medicine, 8) hepatology, and 9) other indications. Detailed information can be found in [Section 8.6.3](#).
- c. Overview of prespecified infections and antibiotics can be found in [Section 8.6.3](#).
- d. Earliest of: 1) loss to follow-up, 2) death, 3) end of observation period (the latest available data), or 4) study end date 31/12/2024

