### 8.3. Study population with inclusion and exclusion criteria

#### *Objective 1*

##### Inclusion criteria

- Present in the data source during the period of 01/01/2017 to 31/12/2024.

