#### **United Kingdom: Clinical Practice Research Datalink GOLD (CPRD GOLD)**

CPRD GOLD will be included in this study because it is a primary care data source that provides relevant information on the use of immunoglobulins in the general population.

Based on a preliminary feasibility assessment, the expected number of person counts for immunoglobulin use in CPRD GOLD will be 73,600.

Moreover, data availability and follow-up in CPRD GOLD is sufficient, as data availability starts in 1987, and the date of most recent data extraction is 05/2025, which aligns with the study period. The median follow-up of the first observation period is 2,150 days.

There are no study specific limitations present in CPRD GOLD.

Lastly, CPRD GOLD has blanket approval, which makes the execution of this study feasible within the current study timelines.

Table S1. Fitness-for-use assessment of data sources.

Design elements	Operational definition	Data elements for valid capture	Criticality of the quality of the element, including justification where relevant	Suggested extensiveness assessment	Suggested assessment of other quality dimensions	Suggested substantiation by documentation
Study population	General study population ( obj. 1 )	N/A	N/A	N/A	N/A	N/A
	Population with an immunoglobulin prescription ( obj. 2–4 )	Prescription of immunoglobulin treatment (RxNorm code)	High	100% will have an immunoglobulin prescription, the expected number of persons counts for immunoglobulins in the data sources included in this study range from 10,900 (CDW Bordeaux) to 73,600 (CPRD GOLD).	100% of prescriptions have been mapped to RxNorm	N/A
Treatment/exposure	Immunoglobulin prescription	Prescription of immunoglobulin treatment (RxNorm code)	High	N/A (to be assessed on a research question basis)	N/A	N/A
Comparator group (not relevant)	N/A	N/A	N/A	N/A	N/A	N/A
Key outcomes per objective	Immunoglobulin prescription ( obj. 1 )	Prescription of prespecified immunoglobulin treatment (RxNorm code), including, if available, route of administration	Medium	Immunoglobulin prescriptions are included in all data sources. The expected number of persons counts for immunoglobulins in the data sources included in this study range from 10,900 (CDW Bordeaux) to 73,600 (CPRD GOLD).	N/A	N/A

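### Objective 1 fixes age once, at cohort entry, yet reports annual prevalence by age group over eight years, so the later age-specific figures increasingly describe the wrong ages

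*Protocol*

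**What the plan says.** Section 8.6.3 gives the objective 1 age strata (1 to 18, 19 to 65, over 65) under the rule "Age groups, defined at cohort entry date". The notes to Figure 1a in Section 8.1 say the same: stratification by sex or age group "will be done at cohort entry date".

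The objective 1 population in Section 8.3 is anyone who meets a single criterion: "Present in the data source during the period of 01/01/2017 to 31/12/2024". Section 8.2 lets follow-up run to 31/12/2024 at the latest. On the estimates, Section 8.8.3 states: "Prevalence will be calculated as overall and annual". Section 8.8.4 lists this figure among the outputs: "Annual prevalence of immunoglobulin use, stratified by ingredient and age group, per data source".

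No section updates age by calendar year or sets a separate entry date for each year or each age band.

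**The concern.** Age at entry describes a person correctly only near the time of entry. When one entry age labels up to eight annual estimates, each stratum ages like a closed cohort and is topped up only by people who join the source later. A person aged 60 on 01/01/2017 is counted in 19 to 65 in every year through 2024, when that person is 67.

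The planned figure of annual prevalence by age group would be read as the prevalence in people of those ages in each year, and Section 8.8.3 says that trends over the study period are the aim. Under the stated rule, a change within a stratum mixes real change in immunoglobulin use with the ageing of the people in it. A reader could not separate the two.

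**Working it through.** The protocol gives no figure of its own on this point, so the check is to follow the stated rule forward in time.

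**Inputs from the protocol**
- Age fixed at cohort entry (Sections 8.1 and 8.6.3).
- Eight calendar years: "The study period is from 01/01/2017 to 31/12/2024" (Section 8.5).
- Bands in completed years: 1 to 18 covers [1, 19), a width of 18 years; 19 to 65 covers [19, 66), a width of 47 years.
- Median length of the first observation period (Annex II): 2,150 days in CPRD GOLD, 247 in CDW Bordeaux, 116 in IQVIA DA Germany.

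**Assumptions not in the protocol**
- Ages are uniform within each band.
- Leaving the source does not depend on age within a band.
- Cohort entry for someone already present is 01/01/2017.

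**Share past the upper bound.** After *t* years the share of an entry cohort that has outgrown its band is *t*/18 for 1 to 18 and *t*/47 for 19 to 65. For people present since 01/01/2017:

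| Date | *t* | 1 to 18, now 19 or older | 19 to 65, now over 65 |
|---|---|---|---|
| Start of 2018 | 1 | 5.6% | 2.1% |
| Start of 2020 | 3 | 16.7% | 6.4% |
| Start of 2022 | 5 | 27.8% | 10.6% |
| Start of 2024 | 7 | 38.9% | 14.9% |
| Mid-2024 | 7.5 | 41.7% | 16.0% |

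At the start of 2024 the members of the 1 to 18 stratum who entered in 2017 are aged about 8 to 25.

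**Share of the whole 2024 stratum.** The protocol does not say what fraction *f* of the 2024 denominator entered in 2017. If everyone else is correctly placed, the misplaced share at the start of 2024 is *f* × 7/18 or *f* × 7/47:

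| *f* | 1 to 18 | 19 to 65 |
|---|---|---|
| 25% | 9.7% | 3.7% |
| 50% | 19.4% | 7.4% |
| 75% | 29.2% | 11.2% |
| 100% | 38.9% | 14.9% |

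**By data source.** Setting *t* to each source's median first observation period:
- CPRD GOLD: 2,150/365.25 = 5.89 years, giving 5.89/18 = 32.7% of the 1 to 18 group past its bound.
- CDW Bordeaux: 247/365.25 = 0.68 years, giving 3.8%.
- IQVIA DA Germany: 116/365.25 = 0.32 years, giving 1.8%.

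These medians are not stated to be limited to 2017–2024, so they rank the sources and do not estimate the misplaced share.

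**Effect on a prevalence.** If a share *m* of the 1 to 18 stratum are really young adults, and prevalence in young adults is *r* times that in children, then reported/true = (1 − *m*) + *m r*. The protocol gives no value for *r*, so these are illustrations only. With *m* = 20%, the ratio is 0.9 for *r* = 0.5, 1.2 for *r* = 2 and 1.4 for *r* = 3. There is no distortion if *r* = 1.

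**The case against.** The strongest reply is that the protocol never defines the cohort entry date for objective 1. Section 8.2 gives a follow-up start for the other objectives but not for this one. If entry meant entry into each age-specific denominator, nobody would be misplaced, and the *IncidencePrevalence* package may handle age in some such way. The lack of a definition is real. But that reading appears nowhere in the text, and it fits poorly with sex being defined at the same date in the same list, since sex has no band to move into. If the package does update age, the text misdescribes the analysis and still needs correcting.

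Several points about size stand:
- The 42% and 16% apply to people present throughout since 01/01/2017. They are not shares of the full 2024 strata.
- Annex I says that the number of contributing practices in England is dropping in CPRD GOLD, which works against continuous presence.
- Median observation is under one year in the other two sources, so the effect there is small.
- Misplacement biases a prevalence only if use differs between those just past a boundary and the rest of the band, and the protocol gives no figures on that.
- Everyone over 65 at entry stays over 65. That stratum only lacks the people who pass 65 after entering.
- All-age prevalence, results not split by age, and objectives 2 to 4 are untouched.

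These points limit how far the problem reaches. They do not make the stated rule suit the planned figure.

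**Conclusion.** The concern holds. The protocol states a specific rule twice, and that rule does not fit an output it promises, so this is more than a detail left to a later document. Among people present since 01/01/2017, up to 42% of the 1 to 18 stratum and 16% of the 19 to 65 stratum are outside their labelled ages by mid-2024, assuming uniform ages within bands and no age-dependent exit. If 25% to 75% of the 2024 denominator entered in 2017, the start-of-2024 shares are about 10% to 29% and 4% to 11%. The problem lies mainly in CPRD GOLD, which also has the largest expected immunoglobulin count (73,600, Section 8.7). Because the share rises every year, it bears directly on the age-specific trends. The change should be made before the analysis is run; it does not put the rest of objective 1 in doubt.

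**What to change.** In Sections 8.1 (notes to Figure 1a) and 8.6.3, state that for annual estimates age is taken on 1 January of the calendar year in question, or that people move between age strata on their birthdays. With the first option, the share outside the labelled band at the start of each year is zero by construction. Keep age at cohort entry only for the overall 2017–2024 estimate, label it as such, and define the objective 1 cohort entry date in Section 8.2. Check that the analytical code applies the same rule. Age at index date for objective 4 needs no change. The cost is one sentence in each of Sections 8.1 and 8.6.3 and a short definition in 8.2, with no new data.
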